10.5 Missed Doses

Study staff will provide adherence support to CAB-LA participants. When doses are missed, study staff will follow the applicable guidelines. Providers will work pro-actively and prospectively identify periods during which participants are likely to miss doses (eg travel). Participants will be provided with oral bridging prevention medication (TDF-FTC) to cover these periods. Upon return to clinic for planned or unplanned missed doses, CAB-LA dosing will be as per protocol below.

- a. If a scheduled injection visit is missed or delayed by more than 7 days, the study

clinician will determine when resumption is appropriate.

b. Recommended Dosing after a missed visit is detailed in **Table 7**.

Table 7. Missed Dosage Recommendations

Time since Last Injection	Recommendation
If second injection is missed and time since first injection is:	
Less than or equal to 8-weeks	Administer 600-mg (3-mL) gluteal intramuscular injection of CAB-LA as soon as possible, then continue to follow the every 8-weeks injection dosing schedule.
Greater than 8-weeks	Restart with 600-mg (3-mL) gluteal intramuscular injection of CAB-LA, followed by a second 600-mg (3-mL) initiation injection 4-weeks later. Then continue to follow the every 8-weeks injection dosing schedule thereafter.
If third or subsequent injection is missed and time since prior injection is:	
Less than or equal to 12 weeks	Administer 600-mg (3-mL) intramuscular injection of CAB-LA as soon as possible, then continue with the every 8-weeks injection dosing schedule.
Greater than 12-weeks	Restart with 600-mg (3-mL) gluteal intramuscular injection of CAB-LA, followed by the second 600-mg (3-mL) initiation injection dose 4-weeks later. Then continue with the every 8-weeks injection dosing schedule thereafter.

10.6 Contraindications. CAB-LA is contraindicated in individuals:

- a. With unknown or positive HIV-1 status
- b. With previous hypersensitivity reaction to cabotegravir
- c. Receiving the following co-administered drugs for which significant decreases in cabotegravir plasma concentrations may occur due to uridine diphosphate glucuronosyltransferase:
 - vii. Anticonvulsants: Carbamazepine, oxcarbazepine, phenobarbital, phenytoin
 - viii. Antimycobacterials: Rifampin, rifapentine

10.7 Drug Interactions

- a. **Use of Other Antiretroviral Drugs after Discontinuation of CAB-LA.** Residual concentrations of cabotegravir may remain in the systemic circulation of individuals for prolonged periods (up to 12 months or longer). These residual concentrations are not expected to affect the exposures of antiretroviral drugs that are initiated after discontinuation of CAB-LA
- b. **Potential for Other Drugs to Affect CAB-LA.** Cabotegravir is primarily metabolized by UGT1A1 with some contribution from UGT1A9. Drugs that are strong inducers of UGT1A1 or 1A9 are expected to decrease cabotegravir plasma concentrations; therefore, coadministration of CAB-LA with these drugs is contraindicated
- c. **Established and Other Potentially Significant Drug Interactions.** Information regarding potential drug interactions with cabotegravir is provided in **Table 8** below.

Table 8. Drug Interactions with CAB-LA

Concomitant Drug Class: Drug Name	Effect on Concentration	Clinical Comment
Anticonvulsants: Carbamazepine Oxcarbazepine Phenobarbital Phenytoin	↓ Cabotegravir	Coadministration is contraindicated with CAB-LA due to potential for significant decreases in plasma concentration of CAB-LA.
Antimycobacterials: Rifampin Rifapentine	↓ Cabotegravir	
Antimycobacterial: Rifabutin	↓ Cabotegravir	When rifabutin is started before or concomitantly with the first initiation injection of CAB-LA, the recommended dosing of CAB-LA is one 600-mg (3-mL) injection, followed 2 weeks later by a second 600-mg (3-mL) initiation injection and monthly thereafter while on rifabutin. When rifabutin is started at the time of the second initiation injection or later, the recommended dosing schedule of CAB-LA is 600 mg (3 mL) monthly while on rifabutin. After stopping rifabutin, the recommended dosing schedule of CAB-LA is 600 mg (3 mL) every 8 weeks.

d. **Drugs without Clinically Significant Interactions with Cabotegravir.** The following drugs can be co-administered with cabotegravir (non-antiretrovirals) or given after discontinuation of cabotegravir (antiretrovirals and non-antiretrovirals) without a dose adjustment: etravirine, midazolam, oral contraceptives containing levonorgestrel and ethinyl estradiol, and rilpivirine.

10.8 Drug Overdosage

There is no known specific treatment for overdose with CAB-LA. If overdose occurs, the participant will be treated appropriately, and further CAB-LA continuation determined by the Investigator.

11. HUMAN SUBJECTS PROTECTIONS

11.1 Vulnerable Participants

11.1.1 Pregnant Women and Fetuses

- a. CAB-LA will be used during pregnancy if the expected benefit justifies the potential risk to the fetus. Factors to consider include the long acting nature of CAB-LA, the actual gestational age, adherence, the risk of seroconversion and available data around the safety of study drugs and alternative PrEP regimens in pregnancy and breastfeeding.
- b. In the HPTN 084 trial evaluating cabotegravir long-acting (LA) for pre-exposure prophylaxis (PrEP) in women in sub-Saharan Africa, no birth defects were reported of the 63 women that became pregnant while taking CAB-LA. Given the need for more data on pregnancy and breastfeeding while taking CAB-LA, participants will be monitored closely for side effects during pregnancy and breastfeeding during the study and up to 8 weeks post-partum.
- c. Pregnant participants will sign a consent to be monitored for up to 8-weeks postpartum to ascertain the pregnancy and infant outcomes
- d. Participants will be registered in the Antiretroviral Pregnancy Registry to contribute to the global scientific community's understanding of CAB-LA use in pregnancy and breastfeeding
- e. It is recommended that participants of child bearing potential taking CAB LA should use an effective contraceptive method during the study, through any additional extension phase and for 52 weeks after the last injection if transitioning off CAB-LA, to avoid pregnancy. Participants that are currently on a contraceptive method at CAB-LA start will be informed of the risks and benefits of CAB-LA during pregnancy, if they chose to stop using contraceptives. Participants not on a contraceptive method when starting CAB-LA will be informed about the risks and benefits to CAB-LA during pregnancy if they become pregnant. CAB-LA will not be given to women who are pregnant at time of initial injection; women who become pregnant after starting CAB-LA will be allowed to

remain on CAB-LA during pregnancy, as deemed appropriate by their provider, and will be re-consented for additional follow-up of pregnancy and infant outcomes.

- f. It is not known if cabotegravir is present in human breast milk, affects human milk production, or has effects on the breastfed infant. Participants who are currently breastfeeding will be informed of the risks and benefits in the consenting process, and unknown effects on infants of exposure to CAB-LA through breastmilk.
- g. No dosage adjustment of CAB-LA is necessary for participants with mild (creatinine clearance 60 to <90 mL/min) or moderate renal impairment (creatinine clearance 30 to <60 mL/min). In participants with severe renal impairment (creatinine clearance 15 to <30 mL/min) or end-stage renal disease (creatinine clearance <15 mL/min), increased monitoring for adverse effects will be provided
- h. No dosage adjustment of CAB-LA is necessary for participants with mild or moderate hepatic impairment

11.1.2 Children

Youth aged 15 years and up are among the populations most in need of improved HIV outcomes and are a group targeted for participation this study. The Uganda National Council for Science and Technology (UNCST) has determined that individuals aged ≥ 14 years are able to provide independent consent for research if they have a sexually transmitted infection. In Uganda and Kenya, children of the age represented in this study can obtain HIV testing services and HIV care without parental consent if considered independent or an emancipated minor.

Participants aged 15-17 taking part in HIV prevention procedures (CAB-LA Extension) and those taking part in the surveys who are not considered mature or independent minors will be required to sign an assent form, with separate parental consent. Information discussed in study visits and test results, including for HIV or STI testing, will not be disclosed to parent/guardians.

As with adults, participants <18 years will be given sufficient time to read or be read the consent form in their language and to ask any questions. None of the diagnostic tests or procedures provided in the study are more harmful to youth as compared to other groups.

11.1.3. Illiterate Participants

The study will enroll participants who may be economically or educationally disadvantaged. Participants in rural populations and those who are educationally disadvantaged are among those most at risk in their country for poor HIV care outcomes, and it is important to provide opportunities to participate in research to all people independent of their literacy. If a potential study participant is unable to read or write, his or her fingerprint will substitute for a signature, and a signature from a witness to the informed consent procedures will be obtained. Participants taking part in activities for which a verbal consent is required will have the consent text read to them in their language. As with other groups, illiterate participants will be provided sufficient time to be read the consent form or ask questions in order to understand study procedures.

12. RISKS

Privacy: The primary risk to study participation is breach of privacy. Care will be taken to protect the privacy of participants and parents/guardians. However, there is a risk that others may inadvertently see patients' medical information, and thus their privacy may be compromised.

Psychological Discomfort: There is the possibility of some psychological discomfort that may arise from questions and sensitive issues assessed in the stigma, sexual behavior, and youth life-skills and behaviors surveys and the in-depth qualitative interviews. We will train all study staff involved with surveys and qualitative interviews to recognize signs and symptoms of psychological discomfort and in the use of strategies to minimize such discomfort. This will include reminders that an individual may always choose to not answer any specific question that makes them uncomfortable or to stop surveys and interviews at any time. Referral resources for significant issues will also be made available to study staff should subject referrals to care be desired.

Venipuncture and fingerprick sample collection: Study sampling during testing activities will be done by venipuncture or fingerprick, depending on the assay. The total volume of blood taken per participant, including blood taken for standard health facility evaluations, is too small to for participants to experience any serious side-effects, although a mild and transient feeling of discomfort or bruising may occur at the site of sampling and bruising.

Ensuring Necessary Medical or Professional Intervention in the Event of Adverse Effects: Procedures will be put in place for the referral and care, free of charge, for necessary medical or professional intervention in the event of the unlikely occurrence of severe adverse effects. Care will be provided at local Ministry of Health care clinics or nearby referral hospitals as necessary.

Potential Side Effects of CAB-LA

Most Common Side Effects:

- Pain, tenderness, hardened mass or lump, swelling, bruising, redness, itching, warmth, abscess, discoloration, or loss of sensation at the injection site
- stomach pain
- vomiting
- diarrhea
- muscle pain
- headache
- rash
- fever
- loss of appetite
- tiredness
- drowsiness
- sleep problems
- back pain
- nausea
- upper respiratory infection

Other side effects of cabotegravir may include:

a. Allergic reactions:

- generally ill feeling
- blisters
- tiredness
- muscle or joint aches
- trouble breathing
- fever
- blisters or sores in the mouth
- redness or swelling of eyes
- swelling of the mouth, face lips or tongues

b. Liver Changes

c. Depression or Mood Changes

d. Hypersensitivity to Cabotegravir

Potential Risks associated with Pregnancy and Breastfeeding on CAB-LA:

There is very little information on the safety of CAB-LA during pregnancy and breastfeeding. Participants will need to weigh the risks to their pregnancy and infant to the benefits of their HIV prevention based on the information provided below.

If participants become pregnant during the study and choose to take CAB-LA during pregnancy, staff will help participants understand that we have limited information on the safety of this drug during pregnancy. Of the 63 women who became pregnant while taking CAB-LA in Sub-Saharan African trials, there were no birth defects. However, it is always possible there is some side effect we are unaware of as we learn more about CAB-LA in pregnancy. To ensure CAB-LA is as safe as possible for the mother and baby, we will monitor participants closely during pregnancy and post-partum. Participants will also be required to sign an informed consent that agrees to 8-weeks of monitoring after delivery as part of the safety assessment.

If participants are breastfeeding when they start this study or breastfeed after becoming pregnant on the study and choose to begin CAB-LA, staff will explain that we have limited information on the safety of this drug during breastfeeding. In studies of another drug, called dolutegravir, which is very similar to CAB LA no nursing babies had any problems. These babies were breastfed by mothers who had HIV and who were taking dolutegravir as treatment. Small amounts of dolutegravir were found in the breastmilk. It is possible some CAB-LA may pass to a baby through breastmilk.

CAB LA has been detected in the systemic circulation for up to 12 months or longer after an injection and the consequences of this level of exposure to the fetus are currently unknown. Consideration should be given to the potential for fetal exposure during pregnancy, even after the injections have been stopped.

- The safety of exposure of CAB- LA to infants through breastfeeding has not been established.

- Due to the nature of CAB-LA injections, CAB-LA may be present in breastmilk for up to, or beyond, a year after the final injection.
- The clinical consequences of exposure of the infant to CAB-LA are unknown.

While not required, to prevent any risk to the participant's pregnancy or to the infant, it is recommended that participants of child-bearing potential taking CAB-LA should use an effective contraceptive method during the study through any additional extension phase and for 52 weeks after the last injection if transitioning off CAB-LA, to avoid pregnancy.

13. SOCIAL IMPACT EVENTS

Individuals enrolled in this study may experience personal problems resulting from the study participation. Such problems are termed social impact events. Although study sites will make every effort to protect participant privacy and confidentiality, it is possible that participants' involvement in the study could become known to others, and that participants may experience stigmatization, discrimination or, in rare cases, intimate partner violence as a result of being perceived as being HIV-infected or at risk for HIV infection. For example, participants could be treated unfairly, could have problems being accepted by their families and/or communities, or could experience abuse by their partner. Problems may also occur in circumstances in which study participation is not disclosed, such as impact on employment related to time taken for study visits.

In the event that a participant reports a social impact event, every effort will be made by study staff to provide appropriate assistance, and/or referrals to appropriate resources. Social impact events that are judged by the investigators to be serious, unexpected, or more severe or frequent than anticipated, will be reported to the relevant IRBs.

14. BENEFITS

There will be no direct benefit to participants from participating in this study. The enhanced measures to improve oral PrEP, CAB-LA and PEP delivery, if assigned to the group that receives it, may help participants stay on medications, receive care, or reduce the likelihood of acquiring HIV infection, but this cannot be guaranteed. Participation in the study may benefit the community, scientists and doctors who work on providing HIV care in health centers such as in this study.

15. COMPENSATION

Participants will not receive compensation or payment in this study for taking part in research activities, except those participating in in-depth interviews.

16. PARTICIPANT PRIVACY AND CONFIDENTIALITY

Care will be taken to protect the privacy of participants and parents/guardians. Study participants will be identified only by their unique identification number on study documents except those maintained for contact information or consent documents. Participant study documents will be

kept in individual files in secure filing cabinets in the study facilities. Testing results and sample and results transport documentation will be maintained in the local labs but will likewise not contain participant identifiers and will be accessed by study personnel only. After the study is over, all files containing personal identifiers such as participants' names, names of parents, guardians or relatives, and phone numbers and home locations will be destroyed.

In order to ensure data security and integrity, the following measures will be implemented:

- All members of the study team will be educated in the study protocol prior to the onset of the study.
- Detailed Standard Operating Procedures (SOPs) will be written for all project activities and be provided to relevant team members.
- Team members will be thoroughly trained on the SOP's.
- Where applicable, team members will receive additional training on the use of tablet computers.
- All data transcribed from paper will be double data entered or verified.
- All electronic data will be backed up regularly.
- All data will be transferred to the main Data Center in Kampala to the secure server. This sever is backed up on a daily basis and a monthly backup is stored off-site.
- All computers, including the tablets, will be password protected.
- All computers, including tablets, will be locked in a secure room each night.
- Log books and CRF's will be locked in a secure room each night.

17. STUDY DISCONTINUATION

The study may be discontinued at any time by the IRB, NIAID, or other government entities as part of their duties to ensure that research participants are protected.

18. Community Advisory Board, Stakeholders and Communication of Results

We will utilize a multilayered set of boards. These include: a) **stakeholder advisory board** consisting of representatives from the Uganda and Kenya Ministries of Health, IDRC and KEMRI research organizations, and PEPFAR implementing partners at the national and regional level, who will meet after Phase A is complete and prior to initiation of Phase B, and again at the conclusion of Phase B; b) formal **external scientific advisory board** meeting annually that includes experts in HIV prevention and treatment; experts in PrEP and youth in Uganda and Kenya; and experts in economics/development in East Africa; and c) **in-country advisory board** meeting annually with representation of MoH leads from HIV, non-communicable disease, the World Bank, PEPFAR implementing partners and HIV+ persons. Finally, **local community advisory boards** will provide invaluable input and communication with biannual meetings. We will have ongoing communication with the Kenya and Uganda National AIDS program, and with the PEPFAR implementing partners. Results of this study will be shared with the community, stakeholders, and at scientific meetings, with subsequent submission to publication.

19.ADMINISTRATIVE PROCEDURES

19.1 Regulatory Oversight

The proposed extension will be reviewed and approved by the IRBs of all the participating institutions in the U.S., Uganda and Kenya. This includes the UCSF Committee on Human Research (CHR), the Makerere University School of Medicine - Research and Ethics Committee (SOMREC), the Uganda National Council of Science and Technology (UNCST), the Kenya Medical Research Institute (KEMRI). As described in Section 18.0, this study will employ four levels of data and participant safety monitoring including Study Steering Committee oversight, US and host country Institutional Review Board (IRB) review, Data Safety Monitoring Board (DSMB) Review, and External Clinical Site Monitoring. **Table 9** describes event reporting guidelines to individual IRBs overseeing this study.

CAB-LA was very well tolerated in the registration studies. For this extension, SAEs will be captured in the intervention arm and Grade 3 and 4 AEs and non-serious ADRs leading to withdrawal will be captured for participants on CAB-LA. Grade 3 and 4 AEs will be graded and recorded using the NIAID Adverse Event Grading of Severity scale (<https://rsc.niaid.nih.gov/clinical-research-sites/daids-adverse-event-grading-tables>). Clinical Adverse Events not identified elsewhere are described in **Table 10**. The Clinical Management Team (CMT) will be notified of SAEs as soon as possible and will be reported per regulatory guidelines as stated in **Table 9** below.

Table 9. Reporting Guidelines

Institution	Contact information	Type of Event	Reporting Timeframe	Reporting Method
UCSF IRB	UCSF Committee for Human Research [name] [contact]	SAEs/ Grade 3 or higher AEs that change the study risks or benefits, OR necessitates modification to the IRB-approved consent document(s), and/or the IRB-approved application/protocol	Within 10-working days of awareness	Via online reporting system
NIAID	[name], Program Officer, NIH	SAEs or Harm determined to be possibly, probably or definitely related to study intervention Participants administered CAB-LA: All pregnancies	At the time of reporting to IRBs One-week of awareness (Pregnancies)	Email
ViiV	GSK Medical Information, Safety Services & Vendor Management Group	Participants administered CAB-LA:	Within 72 hours of awareness (SAEs and Significant Safety Issues)	All SAEs and Significant Safety Issues: Email

	[contact]	All SAEs and Significant Safety Issues All pregnancies All Liver Events Grade 3 and higher	One-week of awareness (Pregnancies and Liver Events)	notification with SEARCH SAPPHIRE AE CRF, Country-specific SAE Reporting Forms, and attachment with supplemental information Pregnancies: Email notification with Pregnancy Reporting CRF Liver Events (Grade 3+): Email notification with Liver Reporting CRF
KEMRI-SERU	The Scientific and Ethics Review Unit Through The Deputy Director CMR at [contact].	All reportable SAEs, SUSARs, and Harm	Notify/ report to SERU secretariat within 48 hours upon learning of the event and submit the full report within 5 working days of awareness	Via online reporting system to SERU secretariat
PPB	Pharmacy and Poisons Board	All reportable Grade 3 or higher SAEs, SUSARs, and Harm	Report to PPB within 7 working days of awareness	Via online reporting system to PPB ECCT (Expert Committee on Clinical Trials)
MU-SOMREC	Executive Secretary Faculty of Medicine, Research and Ethics Committee [name]	All serious and unexpected events irrespective of relationship	Fatal and life threatening events within 3 working days of awareness and all other SAEs within 7 calendar days	Via Regulatory Manager
NDA	National Drug Authority	All serious and unexpected events irrespective of relationship	Within 7 days of awareness	Via online reporting

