-Hair sample (if CAB-LA received in last 120 days)			X		X	X		X						
-Stored plasma (from 2 cc sample above)		X	X	X	X	X	X	X						
Safety Labs														
-Pregnancy testing ¹	X	X	X	X	X	X	X	X	X	X	X	X	X	X
-ALT Monitoring ^{4, 5}	X		X*		X			X*			X*			X*
Adverse Event Monitoring	X	X	X	X	X	X	X	X	X	X	X	X	X	X
GBV Screening	X				X			X			X			X
Survey and IDI														
-Participant CAB-LA Survey and IDI ²	X				X			X						
-Provider and Clinic Staff DCP-LA Survey and IDI	X				X			X						
Costing³	X	X				X								
For participants who stop CAB LA before end of extension study														
-For 48 weeks from last injection: Recommend oral PrEP (TDF/3TC) to cover tail														
-Switch back to Q12 week visits - HIV RNA and pregnancy testing Q12 weeks														

¹For women who become pregnant, repeat pregnancy tests are not needed. Women who become pregnant during the study will be followed to delivery for assessment of mother and infant status

²Participant survey/IDI will be conducted at start of CAB-LA and Weeks 24 and 48 from time of CAB-LA start or discontinuation.

³Costing will occur between weeks 24-48.

⁴ALT Monitoring will occur at baseline, Week 24 for all participants. *Per provider discretion, ALT monitoring will occur at Weeks 8, 48, 72 and 96.

⁵Bilirubin and additional labs indicated will be tested in the case of ALT increase.

⁶HIV RNA will be drawn at CAB-LA reinduction, as described in Table 6.

⁷Week 48 visits may occur between 40 and 56 weeks after Baseline; Week 96 visits may occur between 88 and 104 weeks after Baseline; only participants on CAB-LA at the Week 48 visit may take CAB-LA between weeks 48 and 96.

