19.5 Adverse Event Procedures and Reporting Requirements

For persons receiving CAB-LA, Grade 3 and 4 AEs will be monitored in addition to SAEs.

Grade 3

Any grade 3 or higher clinical or laboratory AE observed prior to their first injection of active CAB will prompt consultation with the clinical officer (CO) prior to any injectable dosing.

At any time, participants who develop a Grade 3 AE or toxicity that is not specifically addressed in the Table below and is judged to be related to CAB-LA by the Investigator, CAB-LA use will be temporarily discontinued. In general, the investigator will re-evaluate the participant until resolution of the toxicity. For Grade 3 AEs deemed related to CAB-LA, will be permanently discontinued if improvement to severity \leq Grade 2 cannot be documented within 4 weeks of awareness. If CAB-LA is resumed after holding for a Grade 3 AE and the same Grade 3 AE recurs without alternative explanation, CAB-LA will be permanently discontinued. For Grade 3 AEs deemed unrelated to CAB-LA, the participant may continue with appropriate clinical management by the site, per local standards of care.

Grade 4

Any grade 4 or higher clinical or laboratory AE observed prior to first injection will prompt evaluation and may requiring holding of dosage, as determined by the CO and CMT. Participants who develop a Grade 4 AE or toxicity that is not specifically addressed in **Table 11** (regardless of relationship to CAB-LA) will have the CAB-LA injections temporarily discontinued. CAB-LA use will not be resumed if the Grade 4 AE is considered by the Investigator to be related to the injections. If CAB-LA use is resumed and the same Grade 4 AE recurs at Grade 4 level at any time, CAB-LA will be permanently discontinued, unless an alternative explanation for the recurrence is clearly documented.

Pregnancy

Any pregnancy that occurs during in participants taking CAB-LA must be reported using the Pregnancy Reporting Case Report form to NIAID and ViiV Healthcare within **one week** of learning of its occurrence. Pregnancies that are associated with SAEs will be reported within 72 hours using the Adverse Event CRF, Country-specific SAE Reporting form, and supplemental information attached.

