Our secondary objective to evaluate implementation will follow the RE-AIM framework and corresponding measures (defined in Table 4). Analyses assessing the primary measures of Reach, Adoption, Implementation and Maintenance will be based on standard descriptive statistics. Analyses to evaluate Effectiveness will compare covered time over the 48 week CAB-LA extension period to covered time prior to the CAB-LA extension among intervention participants. We will adjust for measured changes in participant characteristics between these two follow-up periods, using a TMLE designed for serial measures. Measures of control participants will also be used to adjust for temporal trends. We will test the null hypothesis that coverage of the DCP model with CAB-LA is the same as coverage of the DCP model without CAB-LA. We will again use a two-sided test at the 5% significance level. Primary analyses will again pool over trials, while secondary analyses will be stratified by trial. In addition, we will evaluate marginal and adjusted predictors of CAB-LA uptake and persistence. Our tertiary objective to evaluate changes in knowledge, awareness, and acceptability/satisfaction will be based on applying TMLE to survey data, accounting for repeated measures.

Additional descriptive analyses will include HIV incidence and safety. HIV seroconversions will be measured in each arm and incidence rates will be calculated using person time at risk. Safety Grade 3 and Higher AEs and SAEs will be measured for participants using CAB-LA and incidence rates will be calculated during person time exposed. These analyses will be complemented with costing evaluations as well as participant and provider qualitative data from IDI.

All analyses of the community-based trial will account for clustering.

21.2 Pharmacokinetic analyses:

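### No collection of new non-serious Grade 3/4 adverse events is planned after a participant leaves CAB-LA, and the person-time for the safety rate is not defined

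*Protocol*

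**What the plan says.** **Who is covered.** Protocol Section 19.1 sets two scopes in one sentence. For serious events, "SAEs will be captured in the intervention arm". For the rest, "Grade 3 and 4 AEs and non-serious ADRs leading to withdrawal will be captured for participants on CAB-LA". Section 19.5 repeats the narrower scope: "For persons receiving CAB-LA, Grade 3 and 4 AEs will be monitored in addition to SAEs".

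**How the rate is formed.** Section 21.1: "Safety Grade 3 and Higher AEs and SAEs will be measured for participants using CAB-LA and incidence rates will be calculated during person time exposed". Neither the protocol nor the SAP defines exposed time. SAP Section 5 plans only numbers and proportions of participants with adverse events, overall and by arm, and gives no window.

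**Where events are asked about.** In Section 8.1 the row "Adverse Event Monitoring" is in Table 6, the schedule for CAB-LA users. Tables 5 and 5a, for people not receiving CAB-LA, have no such row. For those who stop, Table 6 lists a recommendation of oral PrEP for 48 weeks after the last injection and then: "Switch back to Q12 week visits - HIV RNA and pregnancy testing Q12 weeks". Section 8.1 also says that they stay in follow-up, though not beyond Week 96.

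**How long drug persists.** Section 10.7: "Residual concentrations of cabotegravir may remain in the systemic circulation of individuals for prolonged periods (up to 12 months or longer". Section 12 repeats this. Sections 11.1.1 and 12 use 52 weeks after the last injection for the contraception recommendation.

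**The concern.** The protocol treats the period after the last injection as real drug exposure when it discusses drug levels, contraception and oral PrEP, and Section 21.2 plans to study the pharmacokinetic tail. Adverse event collection is the element with no tail window. Section 22 gives a reason for recording Grade 3 and 4 events, that CAB-LA is not yet approved in Uganda or Kenya, and that reason does not lapse at the last injection.

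Two things are at stake. New non-serious Grade 3/4 events in the tail may never be recorded, although the participants are still being seen. And a reader of the reported rate cannot tell which period it describes. Two analysts could take different denominators from the same protocol sentence and report different rates from the same events.

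**Working it through.** The documents give no adverse event rate, count or exposure total, so there is no figure to reproduce. The first step compares the text. The second is an illustration of size.

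**Step 1. What is collected after stopping.**

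| Type of event | Scope in the protocol | After stopping CAB-LA |
|---|---|---|
| Serious events | Intervention arm (19.1) | Still captured |
| Grade 3+ liver events | Participants *administered* CAB-LA (Table 9, manufacturer row) | Still reportable, but no ALT is scheduled in Tables 5 or 5a or in the stop rows |
| Events that led to a hold or stop | Re-evaluated or followed up (19.5, 20.2) | Followed |
| New non-serious Grade 3/4 events | Participants *on*, *receiving* or *using* CAB-LA (19.1, 19.5, 21.1) | No planned collection |

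**Step 2. Effect on the rate under each reading of exposed time.**

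Inputs from the documents: 48 weeks of follow-up; last injection at Week 4, 12 or 20, following the Section 10.4 calendar; 67 days (9.57 weeks) as the coverage period after an injection (SAP Section 3.1); a 52-week tail.

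Assumptions not in the documents: the share *d* of starters who stop; a constant event hazard; Grade 3/4 collection ending 67 days after the last injection (a coverage period borrowed here, not an adverse event rule).

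*Reading A: exposed means on CAB-LA.* Numerator and denominator span the same time, so observed/true = 1.00.

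*Reading B: exposed includes the tail.* With H = weeks of follow-up from first injection and L = week of last injection:

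observed/true = [(1−d)·H + d·min(H, L + 9.57)] / [(1−d)·H + d·min(H, L + 52)]

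With H = 48, L + 52 always exceeds 48, so the denominator is 48. Two worked cells:

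- d = 0.10, L = 20: (0.9 × 48 + 0.1 × 29.57)/48 = 46.16/48 = 0.962
- d = 0.50, L = 4: (0.5 × 48 + 0.5 × 13.57)/48 = 30.79/48 = 0.641

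| Last injection | d = 10% | 20% | 30% | 50% |
|---|---|---|---|---|
| Week 4 | 0.93 | 0.86 | 0.79 | 0.64 |
| Week 12 | 0.95 | 0.89 | 0.84 | 0.73 |
| Week 20 | 0.96 | 0.92 | 0.89 | 0.81 |

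The understatement runs from 1 − 0.962 = 4% to 1 − 0.641 = 36%.

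The assumed end of collection matters little. Ending it 8 weeks after the last injection gives (43.2 + 2.8)/48 = 0.958 and (24 + 6)/48 = 0.625 for the same two cells, or 4% to 38%. With H = 96 and the 67-day rule, the same grid runs from 0.955 to 0.721, or about 5% to 28%.

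**The case against.** The strongest reply is that no passage says collection stops. That is so: the gap is inferred from scope words and schedule rows. The missing row is weak evidence alone, because serious events are to be captured throughout the intervention arm and Tables 5 and 5a show no row for those either. Section 22 speaks of recording Grade 3 and 4 events with no on-drug limit. Section 20.2 asks participants to report rash or allergic symptoms on study and calls for monitoring of behaviour during the study. These points show inconsistent wording, but they do not supply a collection rule. The Section 20.2 text is clinical instruction, and Sections 19.1, 19.5 and 21.1 agree on the narrower scope.

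Four stronger readings are tempting, and the documents do not support them:

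- *The rate has a mismatched numerator and denominator.* This cannot be asserted while exposed time is undefined. Under Reading A they match.
- *Late events in general are lost.* Serious events, Grade 3+ liver events and events under follow-up are still covered.
- *Collection ends at the first missed injection.* Table 7 allows participants to resume after a missed dose, so a missed dose is not the same as stopping.
- *The reported rate would be about 27% to 31% of the truth.* That is the picture for one participant with three injections and a full 52-week tail: 16/(8 + 52) on the Table 6 calendar, 20/(12 + 52) on the Section 10.4 calendar. With exit at Week 48 it becomes 16/48 = 33% or 20/48 = 42%. None of these is the pooled rate.

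Nor do the documents say why people stop. Table 4 lists those reasons as something to be surveyed, so stopping cannot be assumed to reflect poor tolerability. A constant hazard is also generous to the concern, because Section 12 lists injection-site reactions among the common effects and these would not continue at the same rate in the tail.

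**Conclusion.** The point holds in a limited form. Followed as written, the scope statements and schedules plan no collection of new non-serious Grade 3/4 events after a participant leaves CAB-LA, within a period that the protocol itself describes as residual exposure.

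The effect on the safety rate depends on a definition that is missing. With an on-drug denominator there is no bias, but also no planned non-serious Grade 3/4 information on the tail. With a tail-inclusive denominator the rate is understated, by about 4% to 36% over 48 weeks. That range rests on assumed stopping of 10% to 50%, last injection at Weeks 4 to 20 and a constant hazard, so it shows scale and is not a prediction.

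The primary endpoint is untouched, and the rate is one of the additional descriptive analyses in Section 21.1. The change is still worth making, because either reading leaves something unstated and the visits already exist.

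**What to change.** 1. In Tables 5 and 5a, add an adverse event monitoring item at the existing 12-weekly visits for anyone who has ever received a CAB-LA injection, running to a stated time after the last injection or to study exit, whichever is first. The sponsor should choose and justify the window. The documents use 48 weeks (Table 6, oral PrEP) and 52 weeks (Sections 11.1.1 and 12, contraception) for other purposes, and the choice should be reconciled with these.
2. In Section 21.1, define *person time exposed* by that same window, so that events and time are counted over one period, and report the on-injection and tail periods separately.
3. Align *on*, *receiving*, *using* and *administered* across Section 19.1 (including Table 9), Section 19.5 and Section 21.1, and bring the unrestricted statement in Section 22 into line.

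The cost is protocol and case report form wording and one question at visits that already take place. The downside is a few extra background events unlikely to be drug related, which separate reporting of the tail would keep visible. If follow-up has already closed, the denominator can still be defined and the uncollected period stated beside the rate.
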